Official Title

Examining Motivations for and Quality of Alcohol and Marijuana Protective Behavior
Strategy Use: Improving Prevention of Hazardous Young Adult Substance Use

Brief Title

Enhancing Quality in Protective Strategies (EQUIP)

NCT Number

NCT04978129

Unique Protocol ID

7R34AA028730-04

Secondary ID

US NIH Grant/Contract Award Number: 7R34AA028730-04

Document Date

2025-02-03

Protocol Synopsis for Research Project Involving Human Subjects

PROTOCOL INFORMATION

Title of Project: Enhancing QUality In Protective strategies (Project EQUIP) (Phase II)

Name of Principal Investigator: [name]

Institution: University of North Texas Health Science Center, Fort Worth, TX

Department: Health Behaviors and Health Systems, School of Public Health.

Funding Agency / Company (if applicable): NIH/NIAAA

Funding Agency Proposal / Protocol Number (if applicable): R34AA028730A1

A. Purpose of the Study – State the specific scientific objectives of the research, and, if applicable, outline the specific aims.

***Please note that this IRB application is being made only for the Phase 2 Online and Text Message Intervention (Aim 2) of the associated grant proposal. A separate IRB application (IRB approval 2020-139) was submitted and approved for the Phase 1 focus group and cognitive interview portion (Aim 1). Phase 1 was launched in January of 2022, and the results/findings of the focus groups and cognitive interviews are informing the content of the Phase 2 intervention being developed in this proposal.**

The proposed research will (1) collect pilot data to establish feasibility and acceptability and test the interactive online and text message (TM) protective behavioral strategy (PBS) intervention (baseline, 2-month) while also (2) collecting event-level data to examine daily-level associations among PBS motivation/quality, PBS use and non-use, alcohol and/or marijuana use, and negative consequences with a focus on how PBS may differ on concurrent alcohol and marijuana (CAM; use of both substances on the same day, but not so their effects overlap) use or simultaneous alcohol and marijuana (SAM; use of alcohol and marijuana at the same time so that their effects overlap) use days compared to alcohol-only days.

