2-month follow-up assessment. After completion of the 8-week text message intervention, participants will be invited to complete a 2-month follow-up assessment to assess short term effects of the intervention on PBS use (or non-use), motivations for PBS use, quality of PBS use, alcohol use, CAM and SAM use, and related consequences. Participants will be invited via text message and email containing a link to this 2-month assessment. Participants will receive an email shortly before the 2-month follow-up assessment, letting them know that the assessment is approaching. The 2-month follow-up assessment will take approximately 30 minutes to complete. Participants will be paid \$30 to compensate for their time that will be loaded onto their Greenphire MasterCard. If they do not complete the 2-month follow-up survey, we will periodically send reminders via email (up to 8), text (up to 8) and phone call (up to 5). Participants will have 30 days to complete the survey.

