Cannabis use will be measured with a parallel DDQ measure that will assess typical days used and typical number of hours high each day ($\alpha=.97$, Lee et al., 2013). The Marijuana Consequences Questionnaire and a modified version (Lee et al., 2021) will measure a broad range of negative cannabis consequences and evaluations of negative cannabis consequences ($\alpha=.89$). Motives for cannabis use will be assessed by a modified version of the Comprehensive Marijuana Motives Questionnaire (C-MMQ) (Lee et al., 2009). To assess risk for substance use disorder, we will use the Cannabis Use Disorders Identification Test-Revised (CUDIT-R; Adamson et al., 2010; $\alpha=.80$). Cannabis PBS will be assessed using an adapted version of the Protective Behavioral Strategies for Marijuana Scale (PBSM-36; Pedersen et al., 2017; $\alpha=.93$). Concerns related to alcohol or cannabis use will be assessed in the baseline survey using the Card Sorting Task from the Brief Drinker Profile (Miller & Marlatt, 1984). Simultaneous substance use will be assessed with the Other substance use will be assessed for lifetime and past month frequency using the Customary Drinking and Drug Use Record (CDDR; $\alpha=.70-.94$; Brown et al., 1998; Schafer & Brown, 1991) as well as an adapted version that assesses co-use of substances. Readiness to Change Questionnaire (Treatment Version Revised) will be adapted to assess readiness to change cannabis use (Heather & Hönekopp, 2008; SAMHSA, 2019). SAM use: Questions regarding SAM use will be adapted from the Monitoring the Future measure (Johnston et al., 2015): "Within the past 2 months, how often did you use alcohol at the same time as cannabis – that is, so that their effects overlap?" We will use similar items to assess simultaneous substance use with alcohol and other drugs. CAM use: CAM use is determined from the alcohol and cannabis measures (i.e., endorsement of both alcohol and cannabis use within the same timeframe; Lee et al., 2013). The Consideration of Future Consequences scale ($\alpha = 0.80$; Strathman et al., 1994) will assess the level to which participants weigh immediate and distant outcomes due to their consequences. Anxiety and depression will be measured using the PROMIS Anxiety v1.0 and PROMIS Pediatric Anxiety v1.1 Short Form ($\alpha=.96$; Cella et al., 2010). Participants will be asked to report their intentions for using both alcohol and cannabis over the next 2 months. Concerns relating to alcohol and cannabis use will be selected and ranked in the Card Sorting Task in the Baseline survey (Marlatt & Miller, 1984). Usability Items: At the 2-Month Follow-Up Survey, participants assigned to the intervention condition will receive items to assess the usability of the online and text message program. Please refer to Appendix B for measures.

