Daily survey measures. Our strategy is to collect daily reports each morning after intervention participants received TM content (intervention group). Assessment-only control participants will receive daily surveys on the same schedule as intervention condition participants. **Yesterday's**

alcohol/cannabis use: Participants will report the number of standard drinks consumed the previous day, the number of hours they spent drinking, whether they used cannabis, number of sessions used cannabis, and how long they were high. SAM use will be assessed by asking “Yesterday, did you use alcohol and cannabis at the same time—that is, so that their effects overlapped?” (Patrick et al., 2019).

CAM use will be identified by the endorsement of alcohol and marijuana use the previous day, but responding “no” to the SAM use item. **Substance-related consequences** experienced the previous day will be assessed with items from alcohol and cannabis consequences scales. **Motives to use alcohol**

and cannabis will be assessed via modified versions of the Drinking Motives Questionnaire and the Marijuana Motives Questionnaire, respectively (Bonar et al., 2018). For **alcohol**, we will administer items used in our previous daily diary study of alcohol use ([name] et al., 2020). A modified Marijuana Consequences Questionnaire (Lee et al., 2021) will assess **cannabis consequences**, selecting acute items appropriate for daily-level measurement (Linden-Carmichael et al., 2020). We will assess

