Event-level designs using daily surveys produce rich and complex data sets that permit the examination of different types of associations among constructs, and these complex associations can be tested with GLMM. For instance, H2c specifies that on days when individuals' motivations to use PBS are elevated (i.e., higher than their own average level), they will report lower alcohol use. Here, PBS motivations is the predictor (person-centered) and number of drinks consumed that day is the outcome. A cross-level interaction between the predictor (Level 1) and condition (Level 2) can be tested to determine whether this effect is stronger among those in the intervention condition compared to the assessment-only control condition. GLMM specifications can easily be modified for the event-level data to test all the hypotheses specified by H2c and H2d. For instance in H2d, each day will be coded as: neither alcohol nor marijuana, alcohol alone, marijuana alone, CAM, or SAM. Then dummy codes will be created to make specific comparisons (e.g., alcohol alone days versus SAM use days).

3) *Data Storage and Confidentiality* – *Describe where the research data will be stored during the study and how it will be secured. The investigator must take necessary steps to maintain confidentiality of data. This*

includes coding data and choosing an appropriate and secure data storage mechanism which will prevent unauthorized access to data. State who will have access to the data. If data with subject identifiers will be released, specify the person (s) or agency to whom the information will be released and the purpose of the release. For specific language, please refer to the NTR IRB's [Data Storage and Security Guidance](#) document.

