Approximately 240 (120 intervention group participants; 120 assessment-only control participants) subjects at 1 sites in the U.S. will be enrolled/randomized in the study overall.

2) Describe both Inclusion AND Exclusion Criteria. *BE SPECIFIC! Include physical, mental, cognitive, medical, and other relevant Inclusion and Exclusion criteria.*

- 1) Provide first and last name
- 2) Age 18-24
- 3) Live in Texas
- 4) Valid email address
- 5) Valid cell phone number
- 6) Own a cell phone with text messaging capabilities
- 7) Have a schedule that allows for daily surveys
- 8) Have a device that supports Zoom system requirements to participate in online training session
- 9) Willing to receive study notifications and messages

- 9) Typically drink at least 3 days in the past month
- 10) Typically use cannabis at least 3 days in the past month
- 11) Report having at least 1 alcohol-related or 1 cannabis-related consequence in the past month
- 12) Report being in contemplation or action stage based on readiness to change scale for alcohol or cannabis (i.e., not in precontemplation stage)
- 13) If female, not pregnant or trying to become pregnant
- 14) Not currently in treatment for alcohol or substance use
- 15) Willing to participate in online/text message based intervention
- 16) Not having participated in a Phase 1 focus group or cognitive interview
- 17) Must correctly answer attention check questions (i.e., select 2 for "what is 4 minus 2?")
- 18) Be willing to participate in a 30-minute online training session via Zoom Video Communications
- 19) Owns a valid photo ID to present in online training session

The initial screening is conducted online to determine eligibility. Eligibility questions will be embedded in demographic and behavioral questions so as to not make criteria obvious. Rolling recruitment will be used for the proposed study. We will track participants' personal information (home address, phone numbers, date of birth) to ensure that individuals do not participate multiple times. Upon completion of screening and verification procedures, eligible participants will be sent an email with a link to the baseline survey with an embedded PIN unique to that participant. Aim 1 participants cannot participate in Aim 2.

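### The stated baseline/2-month rule for CAM does not exclude SAM and states no same-day condition, so H2b's CAM outcome as written measures co-use in general

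*Combined protocol and SAP*

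**What the plan says.** Section A (Purpose of the Study) defines CAM as "use of both substances on the same day, but not so their effects overlap"; SAM is use with overlapping effects.

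Section E.1, Daily survey measures, follows that definition: "CAM use will be identified by the endorsement of alcohol and marijuana use the previous day, but responding" no to the SAM item. Section E.2 keeps the two apart for H2d: "each day will be coded as: neither alcohol nor marijuana, alcohol alone, marijuana alone, CAM, or SAM".

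Section E.1, Baseline and 2-month follow-up measures, states a different rule: "CAM use is determined from the alcohol and cannabis measures (i.e., endorsement of both alcohol and cannabis use within the same timeframe". The timeframe and the scale of the resulting variable are not given. SAM has its own past-2-month frequency item in the same paragraph ("how often did you use alcohol at the same time as cannabis"), which the CAM rule does not use. On one of the source measures the text says "Cannabis use will be measured with a parallel DDQ measure that will assess typical days used", with typical hours high.

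The 2-month assessment is meant to capture short-term effects on "quality of PBS use, alcohol use, CAM and SAM use, and related consequences". H2b (section E.2) expects reductions in both CAM and SAM over the past 2 months. Its model has two time points, baseline and 2 months, and the condition-by-time interaction is the parameter of interest. Section E.2 also lists CAM among nine behavioural outcomes that will supply base rates and variances for the R01.

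Section F.2 requires "Typically drink at least 3 days in the past month", and sets the same threshold for cannabis.

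**The concern.** One label covers two constructs. In the daily data CAM excludes SAM; in the survey data that feed H2b, nothing stated excludes it. Anyone with SAM use has endorsed both substances in the period and so meets the survey rule.

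Two results are at stake. An H2b finding on CAM could be a change in SAM, or could hide a real change in CAM. A survey-based CAM rate carried into the R01 power calculation would be the rate of all co-use.

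**Working it through.** The plan gives no figure for CAM, so there is none to reproduce. The check compares the rules and then works out what each reading of the survey rule would yield.

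**1. The rules side by side**

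| Place | Same day required? | SAM excluded? |
|---|---|---|
| Section A definition | Yes | Yes |
| E.1 Daily survey measures | Yes (previous day) | Yes (no to the SAM item) |
| E.2 day coding for H2d | Yes | Yes (separate codes) |
| E.1 Baseline and 2-month measures | Not stated | Not stated |

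**2. Possible readings of the survey rule**

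- *Yes/no over a month or more.* Eligibility requires at least 3 drinking days and 3 cannabis days in the past month, so nearly all of the 240 are positive at baseline. A condition-by-time interaction then has almost no baseline variation to work with. Same-day use is not implied. If 3 alcohol and 3 cannabis days fell independently in 30 days, the chance of no shared day would be C(27,3)/C(30,3) = 2925/4060 = 72%; for 10 and 10 days it is 0.6%. Real use probably overlaps more than chance, so these are upper-end figures.
- *Matching typical days on the alcohol and cannabis questionnaires.* This does impose a same-day condition, on typical days. SAM days still count as CAM.
- *Both endorsed and never on the SAM item.* This adds a condition the rule does not state, and it scores a person who has both CAM and SAM as having no CAM.

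**3. Size under the day-matching reading**

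Let s be the SAM share of co-use days (assumed, since the documents give none). Let c and m be the ratios by which CAM and SAM days change. The true CAM ratio is c. The measured ratio is (1 − s)c + s·m. The base rate is overstated by 1/(1 − s).

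| s | Overstatement | SAM ×0.70, CAM unchanged (true 1.00) | CAM ×0.70, SAM unchanged (true 0.70) | Both ×0.70 (true 0.70) |
|---|---|---|---|---|
| 0.25 | 1.33 | 0.75 + 0.25×0.70 = 0.925 | 0.75×0.70 + 0.25 = 0.775 | 0.70 |
| 0.50 | 2.00 | 0.50 + 0.50×0.70 = 0.85 | 0.50×0.70 + 0.50 = 0.85 | 0.70 |
| 0.75 | 4.00 | 0.25 + 0.75×0.70 = 0.775 | 0.25×0.70 + 0.75 = 0.925 | 0.70 |

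If SAM falls 30% and every removed SAM day becomes a CAM day, the measured ratio is 1.00, while the true CAM ratio is 1 + 0.3s/(1 − s) = 1.10, 1.30 or 1.90.

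**4. Reach**

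H2b's CAM test uses only baseline and 2-month data, so it depends on the survey rule. H2c and H2d use the daily rule. The survey SAM outcome has its own item.

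**The case against.** *The section A definition governs the whole study, and the survey wording is undefined rather than contrary to it.* This stands for the same-day half: matched typical days would supply that condition. A reader might infer that the survey variable certainly ignores same-day use, and the text does not go that far. The objection does not rescue the SAM half, because the rule names the alcohol and cannabis measures as its source and gives no exclusion. A past-2-month SAM frequency cannot remove SAM from individual days.

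*The instruments may resolve it.* The same paragraph lists an adapted version of the drinking and drug use record that assesses co-use, within the block of cannabis measures and next to a sentence broken in the extracted text. Its content and Appendix B are not available. This stands as a limit on confidence. Nothing in the text says the instrument defines CAM or separates non-overlapping use.

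*CAM is one of nine secondary outcomes in a pilot, and correctly scored daily data already exist.* This stands, and it limits the severity.

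*The daily surveys cannot simply take over H2b.* This also stands. Section E.1, Daily assessments, starts the intervention arm's surveys only after the online program and feedback are completed, for which 30 days are allowed. It gives controls the same trigger although they receive no program. Every surveyed day in the intervention arm is also a message day. A daily comparison is therefore an on-treatment, surveyed-day estimate, whereas H2b concerns change over the past 2 months.

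**Conclusion.** The point holds, with moderate confidence, as a minor to should-fix matter. On its stated rule, the survey CAM variable is any co-use including SAM, and H2b's CAM result and the survey-based R01 rate inherit that.

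A reader might infer that the error always favours the intervention. The documents do not support this. H2b predicts falls in both CAM and SAM. A fall in SAM alone would appear as a fall in CAM, a fall in CAM alone would be diluted, and equal proportional falls would leave no bias. The direction is unknown in advance.

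A reader might also infer that CAM is compromised throughout. It is not: H2c, H2d, the daily CAM data and the primary feasibility and acceptability outcomes are unaffected.

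The overstatement of 1.33 to 4.0 times and the ratios above rest on assumed SAM shares of 25% to 75%, assumed 30% falls and the day-matching reading. The mismatch between the rules rests on none of these.

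**What to change.** 1. Relabel the baseline/2-month variable as any alcohol and cannabis use and do not report it as CAM, unless the survey measures allow same-day, non-overlapping use to be scored as in section A and the daily rule.
2. Report the condition comparison for CAM from the daily surveys with the daily rule, and SAM days beside it so that switching is visible. Use a day-level logit GLMM with a random person intercept, condition, weekend, sex, age and baseline readiness. Leave out the daily alcohol and cannabis covariates, which define the outcome, and daily readiness, which is measured after randomisation.
3. Label the result as an effect on surveyed days during the 8 weeks, not as H2b's past-2-month change.
4. Take the R01 base rate from the daily surveys, weighted to the week as (Friday + Saturday + 5 × random-day rate)/7, preferably from the control arm, which receives no messages. For example, with assumed rates of 15% on Friday and Saturday and 6% on other days, the unweighted mean is (15 + 15 + 6)/3 = 12.0% and the weighted rate is (15 + 15 + 30)/7 = 8.6%.
5. Report by arm the number randomised without daily data, and reconcile the control arm's start trigger in Daily assessments.

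The cost is wording in the analysis plan plus the reconciliation in item 5; no new data are needed. The downsides are:

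- There is no baseline CAM value.
- The surveys cover 24 of 56 days (43%). Friday and Saturday are 16 of the 24 surveyed days (67%) against 16 of 56 calendar days (29%).
- The intervention arm is surveyed on message days only.
- Intervention participants who do not complete the online program have no survey start under the current text.

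Precision depends on the CAM rate and the within-person correlation, which the documents do not give. Compute it for this random-intercept model before quoting any figure.

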Our prior research shows that young adults perceive TMs with personally, self-selected alcohol PBS as more useful than PBS chosen at random or selected by researchers ([name] et al., 2018). Thus, it is beneficial to tailor PBS interventions to optimize perceived relevance and to increase motivation to use PBS and to implement PBS with high quality. As such, participants will be asked in the online program evaluation survey to choose 12 alcohol PBS and 12 cannabis PBS that they are motivated to use (from a list of possible PBS for alcohol and cannabis). Participants will also identify whether they prefer to receive that alcohol or cannabis PBS content during the week and/or on the weekend, and at what time of day they would like to receive the PBS. For each self-selected PBS, the interactive online intervention will prompt them to provide information about why they selected that particular PBS. Participants may also receive a series of interactive text messages related to the PBS text messages they receive (i.e., On a scale of 1-5, how useful did you find the strategy that you received?).

Finally, participants will receive information about the daily surveys they will be receiving for the 8-week intervention survey.

The expected length of time to complete the online intervention is 20-30 minutes.

Participants will be asked to provide brief feedback on the personalized information by responding to 2 items presented after each module that will assess how useful and enjoyable the content was.

If participants do not complete the online intervention and feedback on personalized information, we will periodically send reminders via email (up to 6), text (up to 6) and phone call (up to 5). Participants will have 30 days to complete the online intervention and feedback on personalized information.

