Next, the self-selected personalized intervention content will be delivered via text messages (TMs) three days a week (Friday, Saturday, random day [i.e., Sunday through Thursday]) over eight consecutive weeks, to begin the first Friday following completion of the interactive online program and feedback. Participants will report on PBS use and non-use, including motivations and quality of PBS use, and alcohol and cannabis use in daily online surveys timed to occur the day after the intervention messages (Saturday, Sunday, morning after random day). Intervention content will be linked with the data entry module for the baseline and daily assessments, allowing data to be imported into the intervention content (online or TM). Please see Appendix C for a bank of the alcohol and cannabis PBS text messages.

On days intervention group participants will be receiving TM intervention content, they will respond to items in the daily survey assessing readiness to change, willingness to use PBS, and which types of PBS they are interested in receiving that day. Survey items will ask participants to complete a readiness ruler assessing importance of “at this moment” making a change in their alcohol use and cannabis use. Then, a second series of survey items requests a response to a modified readiness ruler assessing willingness to use PBS in general, willingness to use PBS to reduce use, and willingness to use PBS to reduce consequences, separately for alcohol and for cannabis (e.g., “How willing are you to use a tip or strategy related to your alcohol use today (Not at all Willing-Extremely Willing”). Later that day, the PBS content they receive will be personalized and matched to their importance/willingness ratings and reasons to use PBS, such that intervention TM content is stage-appropriate and for reasons related to lower use or lower risk.

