Assessment-only control condition. The assessment-only control condition will not receive any intervention content (online or text message) during the 8-week period of data collection to support testing primary aims. Assessment-only participants will complete all surveys: baseline, 2-month, and daily surveys according to the same schedule as the intervention group.

Online Program Evaluation survey. The intervention condition participants will provide their feedback on the interactive online program. After viewing the online program, they will first be prompted to select which specific PBS they are interested in receiving, will be shown quality and consistency examples of each strategy, and will select which days/times they are interested in receiving a text message relating to each type of strategy. A modified System Usability Scale (Brooke 1996, 2013; Sauro, 2011) and Website Analysis and Measurement Inventory (WAMMI; Danielson et al., 2016) will assess perceived usability of the online intervention and TMs, perceived favorability of the online design, ease of navigation and use, convenience, relevance and usefulness. Perceived viewing, engagement and appeal of the intervention and TMs will be assessed ([name] & Neighbors, 2015; Li et al., 2019; Shrier et al., 2018). Intervention participants will complete items to evaluate the online portion’s: content (thought-provoking, easy to understand, relevant, useful), format (attention-grabbing, interesting, enjoyable) and next steps (motivation to change self/others, open-ended question on most useful and engaging portion of the online feedback session). PBS use intentions, as well as alcohol and cannabis use intentions will be assessed. We will assess if participants were under the influence of alcohol or cannabis while completing

the interactive online program or feedback on personalized information. Please refer to Appendix B for measures.

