Feasibility and acceptability for TM content. This information is subject to change based on the feedback collected from the focus groups/cognitive interviews being conducted in Phase 1. TMs will consist of a two-way dialogue, to assess whether participants read the message, participant response after reading TMs, whether alcohol or cannabis was being used when TMs were sent/read. Adherence will be calculated by the percentage of TMs that prompted a participant response ([name] et al., 2018). Participants will respond by indicating helpfulness, likeability, thought-provoking, and clarity (e.g., 1 = not at all to 5 = very). We will track message timing, response, recall, and content of messages to determine factors that may impact intervention efficacy as well as alcohol or cannabis use. We will examine response rates to intervention TMs on days alcohol and/or cannabis use were reported.

2) **Data Analysis and Data Monitoring** - *Describe plans for statistical analysis of data when appropriate. If a data safety monitoring committee is appropriate to protect the safety and/or welfare of subjects, describe its operation (e.g., membership, stopping rules and frequency of review).*

Data Analysis and Power.

Prior to any inferential statistics, univariate and bivariate descriptive statistics will be used to examine distributions and simple associations among variables. Preliminary analyses will include nature of missing data and identification of extreme values. Baseline equivalence on PBS, alcohol, and cannabis measures and demographic representation across conditions in Phase 2 will be examined. Feasibility and acceptability will be the primary outcomes for Aim 2. Behavioral alcohol and cannabis outcomes (PBS use, PBS motivation, PBS quality, alcohol use, alcohol consequences, cannabis use, cannabis consequences, CAM use, SAM use) will provide estimates of base rates and variance in outcomes to determine power for a R01 application as this program of research transitions to a Stage II study.

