Acceptability of the intervention will also be determined by: (1) proportion of eligible young adults enrolled (80% of eligible young adults agreeing to participate); (2) young adult participants' ratings of individual intervention components including both online and text message content (rating content as favorable overall, attention-grabbing, interesting, enjoyable), (3) young adult participants' ratings of accessibility (acceptable length of intervention, acceptable timing of intervention delivery), usability (ease of viewing and navigating intervention online and via TM), convenience (mode of intervention delivery), and relevance of intervention content (engaging and helpful content, thought-provoking), and (4) the proportion of young adults who would recommend the program (outside of a paid research study). Acceptability will be achieved if 80% of responses in each domain are rated a 4 or higher (out of 5). For the System Usability Scale, scores below 4.0 on the 5-point items indicate a need to re-examine intervention features, and scores of 68 or higher of the 100-point total support overall usability. In the case that intervention areas do not meet these criteria, the investigative team will revise intervention components prior to a future large-scale randomized trial. The Website Analyses and Measurement Inventory (WAMMI) consists of 20 validated statements used to evaluate websites or intervention programs. We will use this measure to assess acceptability of our online and text message intervention. Each statement is rated on a 5-point scale from strongly agree to strongly disagree and scores are calculated for Attractiveness, Controllability, Efficiency, Helpfulness and Learnability as well as an overall global usability score. All scores are automatically calculated by the WAMMI website and compared to large international database of scores for other projects. A global usability score of 50 or higher indicates that a given website or intervention program is above average (50) for usability and accessibility according to a large international database maintained by the creators of the Website Analyses and Measurement Inventory.

H2b: We expect that receiving the intervention will be associated with short-term (2-month) increases in PBS use, motivations for PBS use, and quality of PBS use as well as decreases in motivations for PBS non-use and reductions in past 2-month alcohol use, CAM and SAM use, and related consequences.

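### Text-message usability and appeal items sit in a survey completed before the first message is sent, and the acceptability thresholds do not say which ratings count

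*Combined protocol and SAP*

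**What the plan says.** Section E.2 (Data Analysis and Power) states: "Feasibility and acceptability will be the primary outcomes for Aim 2".

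Section E.1, under Online Program Evaluation survey, describes what intervention participants complete after viewing the online program. It says that the modified SUS and the WAMMI "will assess perceived usability of the online intervention and TMs", and then: "Perceived viewing, engagement and appeal of the intervention and TMs will be assessed".

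Section E.1, under Intervention Condition, says that "participants will be asked in the online program evaluation survey to choose 12 alcohol PBS and 12 cannabis PBS". It schedules the text messages "to begin the first Friday following completion of the interactive online program and feedback".

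Other ratings come later. The Usability Items entry among the baseline and 2-month measures (E.1) says that intervention participants at 2 months "will receive items to assess the usability of the online and text message program"; it names no instrument and refers to Appendix B. H2a in E.2 takes its acceptability ratings from the feedback stage and from assessments after the messages. Replies to the messages themselves are rated for helpfulness, likeability, thought provocation and clarity (Feasibility and acceptability for TM content in E.1, and again in E.2).

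The acceptability paragraph of E.2 relies on "ratings of individual intervention components including both online and text message content" and on accessibility, usability, convenience and relevance. It requires at least 80% of the responses in a domain to score 4 or 5 out of 5. It also sets an SUS total of 68 and a WAMMI global score of 50 as favourable marks. No threshold is attached to an assessment time.

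**The concern.** A usability or appeal rating of a text-message program means something only once messages have arrived. Before that it records an expectation, given here in the same survey in which participants select their own content and delivery times. Some of the E.2 domains, such as whether delivery timing was acceptable and how easy messages were to view, cannot be judged from experience at that point.

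The thresholds have a practical use: under E.2, components that miss them are revised before a larger trial. If expectation ratings are allowed into the message verdict, a text component that participants came to dislike over eight weeks could pass and go forward unrevised. The reverse error is also possible if expectations were lower than experience.

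**Working it through.** The plan gives no figure to reproduce. The check sets the scheduled events in order and then asks which ratings the thresholds admit.

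**Order of events for the intervention arm**

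1. Baseline survey and randomisation (E.1).
2. Online program (E.1, Intervention Condition).
3. Online Program Evaluation survey: strategies, days and times are chosen; SUS, WAMMI and appeal items are worded to cover the messages (E.1).
4. First Friday afterwards: messages begin, 3 days a week for 8 weeks, so 3 × 8 = 24 message days, with ratings by reply.
5. 2-month survey, after the 8 weeks, with usability items on both components.

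Step 3 must precede step 4 whatever the word feedback covers in the scheduling sentence, because the messages are built from choices made in step 3. Message days elapsed at the step 3 rating: 0 of 24, for all 120 intervention participants.

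**Which ratings can enter each threshold**

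- SUS 68 and WAMMI 50: the only survey for which these scales are named is step 3. The 2-month items are unnamed.
- 80% rule: no time point is given, so ratings from steps 3, 4 and 5 are all admissible.
- Reply ratings (step 4) overlap with the relevance domain. They do not cover usability by text, convenience or delivery timing, and they come only from messages that were answered. For those domains, the post-exposure evidence rests on the 2-month survey.

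**Illustration of what pooling could do (all rates assumed)**

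Let *w* be the share of pooled responses given before messages began, with 90% favourable before and 70% after.

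Pooled share = 0.70 + 0.20*w*, which reaches 0.80 when *w* = (0.80 − 0.70)/(0.90 − 0.70) = 0.50.

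- Equal counts: (0.90 + 0.70)/2 = 0.80. Pass.
- All 120 rate before and 90% (108) rate at 2 months: (0.90 × 120 + 0.70 × 108)/228 = (108 + 75.6)/228 = 80.5%. Pass.
- One rating before, one on each of 24 message days and one at 2 months: (0.90 + 25 × 0.70)/26 = 18.4/26 = 70.8%. Fail.
- After messages only: 70%. Fail, by 10 points.

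Under the same assumed opinions, the verdict turns on a weighting that the plan does not state.

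**The case against.** The strongest reply is that the plan already provides for ratings after exposure in three places: the 2-month usability items, the post-message assessments named in H2a, and the replies to messages. H2a can be read as pairing the feedback stage with the online program and the later assessments with the messages. The survey paragraph opens with feedback on the online program, so its references to messages might list instruments for both components without fixing when the message items are given. The 2-month items are described in nearly the same terms, "items to assess the usability of the online and text message program", and may well be the SUS and WAMMI; Appendix B is not available to settle it.

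Much of this stands. A reader might infer that the message part of acceptability is scored wholly on content never received. The documents do not support that, given the three later sources. Nor do they show that SUS and WAMMI are given only before messages; they are only named there. No section says that ratings are pooled across time, and the last pooled example above shows that pooling need not rescue a poor component. Expectation ratings of relevance and convenience also have some value, though not as a substitute for ratings after use.

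What does not stand is that nothing needs changing. The paragraph is headed as one survey and is tied at its start and end to the online program session. Nothing in E.2 keeps its message ratings out of the thresholds.

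**Conclusion.** The point holds in a limited form. As written, section E.1 places message usability and appeal items in a survey completed with 0 of 24 message days elapsed, and section E.2 sets acceptability thresholds without saying which administration supplies them. Pre-exposure ratings can therefore enter a primary outcome and the decision to revise the text component. The text permits this but does not say it will happen.

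The order of events is certain from the documents. The effect on the result is not: the 90% and 70% rates and the response counts are assumptions, and the pooled result runs from 70.8% to 80.5% depending on weighting. The consequence is bounded, since this is a pilot and a missed threshold leads to revision of components. It is still worth correcting, because the verdict concerns a primary outcome and the correction costs little.

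**What to change.** 1. In E.1, Online Program Evaluation survey: limit the SUS, WAMMI and viewing, engagement and appeal items to the online program.
2. In E.1, Usability Items: name the message versions of the SUS, WAMMI and appeal items in the 2-month survey, where usability items are already scheduled.
3. In E.2, acceptability paragraph: report ratings by time point. Judge the text component only on ratings given after messages began, from message replies and the 2-month survey. Keep the 2-month ratings of the online program too, since the monthly summaries send participants back to one of its modules.

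Cost: items move between two existing surveys and E.2 gains a short rule. Message ratings will depend on completion of the 2-month survey, which may be slightly longer for the intervention arm. If the surveys have already been fielded, the E.2 rule still works as an analysis rule: label the pre-message scores as expectations and leave them out of the message verdict.
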